6.0 STUDY DESIGN AND DESCRIPTION

6.1 Study Design

The total duration of this randomized, multicentre, phase III trial is 24 weeks maximum. It includes six weeks of single-blind placebo administration during the run-in period and 16 weeks of double-blind treatment, followed by a single safety visit (within two weeks) for subjects undergoing the second (final) bronchial biopsy.

This trial will be performed in Chronic Obstructive Pulmonary Disease (COPD) patients (GOLD stage II-III, **in Germany stage II only**) and will include two parallel treatment arms (placebo and Roflumilast 500 µg once daily). A 1:1 randomization scheme will be used, i.e. Subjects will be allocated to Roflumilast 500 µg or placebo in equal proportions. Randomization will be stratified by concomitant LABA use.

[figure not shown]
The trial consists of the following periods:

- **Single-blind placebo run-in period** (6 weeks) with visits scheduled at weeks: -6 (V0), -2 (V1) and 0 (V2, randomization visit).
- **Double-blind treatment period** (16 weeks) with visits scheduled at 6, 14, and 16 weeks of treatment (V4-V6). An additional visit V3 will have to be performed within two weeks after bronchoscopy/bronchial biopsy purely as a safety visit. The exact timing of this safety visit will be determined by the Investigator.
- **Safety follow-up.** All adverse events (AEs) will be followed up to 30 days after the double-blind treatment period has been completed. An additional safety visit V7 will be scheduled within 2 weeks after the second bronchoscopy. The exact timing of the safety visit will be determined by the Investigator.

A schematic of the study design is included as [Figure 6.a](#). A schedule of assessments is listed in [Appendix A](#).

Figure 6.a Schematic of Study Design

Single-blind run-in: 6 weeks	Double-blind treatment including Safety follow-up V3 for Subjects undergoing bronchoscopy 16 weeks	Safety follow-up including V7 for Subjects undergoing the second bronchoscopy 2 weeks
---------------------------------	---	--

Therapy consisting of any bronchodilator (SABA, SAMA, LABA, LAMA) or their combination in stable doses. Rescue medication: SABA or SAMA

Abbreviations: V2 – randomization visit and first bronchoscopy, V6 – visit at the end of double blind treatment period and second bronchoscopy, LABA – Long-Acting β_2 -Agonist, LAMA – Long-Acting Muscarinic Antagonist, SABA – Short-Acting β_2 -Agonist, SAMA – Short-Acting Muscarinic Antagonist, o.d. – once daily

6.2 Justification for Study Design, Dose, and Endpoints

It is hypothesized that Roflumilast would reduce the characteristic airway inflammation in patients with COPD (GOLD stage II-III, in Germany stage II only) treated for 16 weeks in a double blind, parallel group, randomized, placebo controlled trial.

Chronic obstructive pulmonary disease (COPD) is an inflammatory condition clinically characterized by progressive, not fully reversible airflow limitation and an accelerated decline in lung function [10]. The role of inflammatory cells in development of COPD was described and it could be shown that reductions of inflammatory cells correlated with clinical improvements [4, 11]. A specific pattern of inflammation in the airway and lung parenchyma of COPD patients could be observed, with increased number of monocyte/macrophages (CD68+), T-lymphocytes with the predominance of cytotoxic CD8+ T-cells and in more severe stage of the disease B-lymphocytes with an increased number of neutrophils in the lumen [4]. The concentration of several inflammatory mediators such as interleukin-8 (IL-8), tumour necrosis factor- α (TNF- α), neutrophil elastase and E-selectin is increased. Inflammatory mediators are being produced not only by the inflammatory, but the structural cells of the airways and the lung as well [5].

GOLD identifies a pressing need to develop agents that suppress the inflammation associated with COPD and prevent the progressive decline in lung function [2].

Roflumilast has shown in clinical studies to improve lung function and reduce COPD exacerbations. The purpose of the present trial is to better understand the anti-inflammatory effects of the drug Roflumilast in the target organ, the lungs, as well as in sputum and in the systemic circulation. Hence, this trial offers the opportunity to address these critical issues by ascertaining potentially important biomarkers and other surrogate endpoints to a clinical patient benefit, while simultaneously identifying anti-inflammatory treatment effects within patients suffering from COPD. Thereby better understanding of the pathophysiology of COPD, which will also be relevant for the development of further new anti-inflammatory COPD treatments. As primary and key secondary parameter the above described CD8+ T-cells and CD68+ cells were selected to be measured in the submucosa as most promising and relevant targets.

Bronchoscopy is a relatively safe procedure. Serious risks from bronchoscopy, such as an air leak or serious bleeding are reported in less than 5 % of procedures. Other risks associated with the procedure are as follows: bleeding, discomfort and coughing, reduced oxygen, lung leak or collapse (pneumothorax) [12]. Bronchoscopy has an invaluable place in airway research. Given that the safety of the volunteer Subject is of paramount importance, the conduct of the clinical trials should be based on well established methods [13]. The individual risk to the Subjects from the bronchoscopy/bronchial biopsy procedure is as minimized based on several principles implemented within the protocol. The bronchoscopy and bronchial biopsy will only be conducted at experienced investigational sites which have shown in previous clinical trials to be capable of performing bronchoscopies in a standardized and safe manner. The same predefined, standardized procedures will be followed, the sites will be individually trained on the trial related procedures, and the quality of the biopsied material will be validated for each site. Dedicated safety follow-up visits have been implemented in the trial schedule subsequent to each visit with a bronchoscopy assessment. In addition, the sputum collection sampling has been separated from the bronchoscopy visits in order to not perform too many interventions on the same day.

A treatment regimen with a once daily dose of Roflumilast 500 µg was effective and safe in several clinical trials assessing COPD patients of GOLD stages II-IV. DAXAS[®] (Roflumilast 500 µg) was approved in the European Union by the European Commission on 5 July 2010 for the maintenance treatment of severe COPD (FEV₁ post-bronchodilator less than 50% predicted) associated with chronic bronchitis in adult patients with a history of frequent exacerbations as add on to bronchodilator treatment. In the U.S.A., Roflumilast 500 µg (DALIRESP[®]) was approved by FDA on 28 February 2011 as a treatment to reduce the risk of COPD exacerbations in Subjects with severe COPD associated with chronic bronchitis and a history of exacerbations.

This is a randomized, double-blind, placebo-controlled trial. Since all Subjects will continue to receive their bronchodilator standard therapy (e.g. LABA and/or LAMA in stable doses) placebo-treatment does not bear any additional risk. The placebo arm is thus ethically justified. All Subjects will be encouraged to contact their Investigator in case of a deterioration of their disease.

After drop-out and/or end of trial treatment Subjects will be treated according to their individual needs and no longer under standardized conditions.

In this clinical trial spirometry assessments will be performed to characterize the disease stage and the disease progress of the enrolled COPD patients. Patients with moderate to severe stage of COPD (stage II and III) will be enrolled; however, no patients with COPD stage IV will be enrolled. (**GERMANY ONLY:** Patients with moderate stage of COPD (stage II) will be enrolled; however, no patients with COPD stage III and IV.) It can be expected that COPD patients with GOLD stage II-III (**in Germany stage II only**) are in a stable health condition to safely undergo the bronchoscopy with bronchial biopsy and sputum collection during the trial. For the same reason patients with a history of a recent exacerbation will be excluded from trial participation.

For biomarker studies in clinical trials, it is important to have relatively easy access to the samples containing the biomarker. The collection of blood serum for analysis is based upon the hypothesis that low-grade systemic effects, including inflammation and oxidative stress, play an important role in the pathogenesis of COPD. A number of markers for systemic inflammation have been shown to be associated with smoking and reduced FEV₁ [14]. Just like blood, induced sputum offers an opportunity to obtain samples containing important disease characteristics with relatively easy access [15]. Many COPD patients produce sputum spontaneously, but because spontaneously produced sputum often contains a large proportion of dead cells, which complicates measurements, induced sputum is the present procedure of choice. The biomarkers provided in the Multi-Analyte Profile (MAP) Human InflammationMAP[®] v.1 (see Section 9.1.17.2) and their distribution will be analysed in blood serum and induced sputum. The cell counts for neutrophils, macrophages, eosinophils and lymphocytes in sputum will be analysed and will serve as a surrogate for airway inflammation. In a 4-week trial, Roflumilast treatment reduced the number of neutrophils and eosinophils, as well as soluble markers of neutrophilic and eosinophilic inflammatory activity in induced sputum samples of patients with COPD [16]. Additionally, it was recently shown that Roflumilast significantly reduced the endotoxin-evoked influx of neutrophils, eosinophils, and total cells into the bronchoalveolar compartment in healthy volunteers [17]. In the present trial, for the first time treatment effects of Roflumilast can be associated to biomarkers in blood and sputum, and effects in the target organ, the lungs.

This trial includes a six-week single-blind run-in period to assess Subjects' compliance and for reasons of standardization. The treatment phase is for 16 weeks. Early effects on airway inflammation may already be shown after four weeks [16]. However, in clinical trials up to one year Roflumilast showed consistent and sustained improvements in lung function and reduction of exacerbation rates [7]. Based on these clinical trial results the treatment duration of 16 weeks can be considered an acceptable time frame to collect information on the anti-inflammatory effect of Roflumilast and allows sufficient time in between the bronchoscopy procedures and sputum collections.

The trial will not be statistically powered to investigate any clinical outcome measures with regard to the efficacy of COPD treatment, but as mentioned above spirometry measurements will be performed to assess Subject pulmonary function and disease progression. The sample size was calculated based on the available information on the primary variable within the literature and kept as small as possible.

In conclusion the trial is considered as adequately designed to show benefits of Roflumilast treatment to patients in terms of anti-inflammatory effects in the target organ, as well as associated to biomarkers in blood and sputum. Multiple safety aspects are incorporated into the trial protocol to minimize the risk to the participating subjects, while simultaneously having the chance to focus the research efforts on a better understanding of the pathophysiology of COPD within patients in need of new anti-inflammatory treatment options. While Roflumilast is an established product for the reduction of COPD exacerbations, its mechanism in the lungs, particularly its anti-inflammatory activities, are not well understood. Better understanding of its effects on inflammatory cells and the inflammatory cascade may result in a better understanding of which patients would benefit most from a treatment with Roflumilast and which measurable parameters (e.g. cell counts, activities, mediators) might serve as surrogate predictors for the clinical efficaciousness of Roflumilast.

6.3 Premature Termination or Suspension of Study or Investigational Site

6.3.1 Criteria for Premature Termination or Suspension of the Study

The study will be completed as planned unless one or more of the following criteria are satisfied that require temporary suspension or early termination of the study.

- New information or other evaluation regarding the safety or efficacy of the study medication that indicates a change in the known risk/benefit profile for Roflumilast, such that the risk is no longer acceptable for subjects participating in the study.
- Significant violation of Good Clinical Practice (GCP) that compromises the ability to achieve the primary study objectives or compromises subject safety.

6.3.2 Criteria for Premature Termination or Suspension of Investigational Sites

A study site may be terminated prematurely or suspended if the site (including the investigator) is found in significant violation of GCP, protocol, or contractual agreement, is unable to ensure adequate performance of the study, or as otherwise permitted by the contractual agreement.

6.3.3 Procedures for Premature Termination or Suspension of the Study or the Participation of Investigational Site(s)

In the event that the sponsor, an institutional review board (IRB)/independent ethics committee (IEC) or regulatory authority elects to terminate or suspend the study or the participation of an investigational site, a study-specific procedure for early termination or suspension will be provided by the sponsor; the procedure will be followed by applicable investigational sites during the course of termination or study suspension.

7.0 SELECTION AND DISCONTINUATION/WITHDRAWAL OF SUBJECTS

Patients with COPD (GOLD stage II-III, in Germany stage II only) are eligible for trial participation.

At least three Subjects per site are required to enable the biopsy sample quality evaluation.

See Section 13.3 for sample size calculation.

All entry criteria, including test results, need to be confirmed prior to randomization or first dose.

7.1 Inclusion Criteria

Subjects meeting the following criteria will be considered for inclusion in the run-in period:

1. Written informed consent obtained according to local regulations before any trial-related activities. A trial-related activity is any procedure that would not have been performed during the routine management of the Subject.
2. History of COPD (according to GOLD 2009) for at least 12 months prior to baseline visit V0 associated with chronic productive cough for at least three months in each of the two years prior to baseline visit V0 (with other causes of productive cough excluded).
3. Outpatients 40-80 years of age.
4. Post-bronchodilator $30\% \leq FEV_1 \leq 80\%$ predicted.
(**GERMANY ONLY:** Post-bronchodilator $50\% \leq FEV_1 \leq 80\%$ predicted.)
5. Post-bronchodilator FEV_1/FVC ratio $\leq 70\%$.
6. Current or former smokers with smoking history ≥ 20 pack years².

7.2 Exclusion Criteria

Subjects meeting any of the following criteria will be excluded from trial enrolment:

Criteria affecting the read-out parameters of the trial:

1. Clinical instability, defined as experiencing a COPD exacerbation six months prior to V0, as indicated by treatment with a systemically administered glucocorticosteroid and/or antibiotics and/or hospitalization.
2. An upper/lower respiratory tract infection e.g. common cold, sinus symptoms, pneumonia, which has not resolved four weeks prior to V0.

² Total pack years = No. cigarettes smoked per day/20 x no. years of smoking. For the purpose of the trial a former smoker is defined as a subject who has not smoked for ≥ 12 months at visit V0. Smoking status will be monitored throughout the trial but not verified by any objective tests.

3. Diagnosis of asthma and/or other relevant lung disease (e.g. history of primary or clinically significant bronchiectases, cystic fibrosis, bronchiolitis, lung resection, lung cancer, interstitial lung disease [e.g. fibrosis, silicosis, sarcoidosis], active tuberculosis) or previous episodes of pneumothorax.
4. Known alpha-1-antitrypsin deficiency.

Criteria within ethical considerations in terms of general health:

5. Duration of oxygen therapy ≥ 12 h/day.
(**GERMANY ONLY:** Any oxygen therapy at home.)
6. History of intubation for COPD or a respiratory failure of any cause in the past year.
7. Hypoxemia defined as oxyhemoglobin concentration $< 88\%$ when breathing room air measured by pulse oximetry.
8. Formal contraindications to sputum collection or impossibility to obtain a sample of sputum valid for analysis.
9. Clinically relevant abnormal laboratory values suggesting an undiagnosed disease requiring further clinical evaluation (as assessed by the Investigator).
10. Suspicion or diagnosis of a bleeding disorders irrespective of its pathophysiological mechanism: Thrombocytopenia (platelets $< 50000/\text{mL}$) and platelet dysfunction (e.g. uraemia), thrombotic or coagulation disorders and bleeding due to abnormal blood vessels (e.g. purpura simplex).
11. Severe psychiatric or neurological disorders.
12. History of depression associated with suicidal ideation or behaviour.
13. Hemodynamic instability (e.g. bradycardia with resting heart rate < 60 beats per min, tachycardia with resting heart rate ≥ 120 beats per min and/or a systolic blood pressure < 100 or > 180 mmHg).
13a) (GERMANY ONLY: Hemodynamic instability (e.g. bradycardia with resting heart rate < 60 beats per min, tachycardia with resting heart rate ≥ 100 beats per min and/or systolic blood pressure < 100 or > 180 mmHg).)
14. History of increased intracranial pressure, superior vena cava obstruction, pulmonary hypertension, aneurysms and arteriovenous malformations within the lungs.
15. Congestive heart failure severity grade IV according to New York Heart Association Functional Classification (NYHA).
15a) (POLAND ONLY: Congestive heart failure severity grade III and IV according to New York Heart Association Functional Classification (NYHA).)

16. Haemodynamically significant cardiac arrhythmias or heart valve deformations.
17. History of angina pectoris (Class \geq II Canadian Cardiovascular Society Functional Classification of Angina Pectoris Scale) or a myocardial infarction within last 12 months, unless corrected with Percutaneous Transluminal Coronary Angioplasty (PTCA) or Coronary Artery Bypass Surgery (CABG) \geq 3 months prior to V0 and asymptomatic since then.
18. X-ray Computed Tomography (CT) or X-ray findings indicating a pulmonary disease other than COPD (e.g. tuberculosis, clinically significant bronchiectases, tumours). CT or X-ray results within 12 months prior to visit V0 are required.
 - 18a) (*GERMANY ONLY*: X-ray Computed Tomography (CT) or X-ray findings indicating an anomaly or pulmonary disease other than COPD (e.g. tuberculosis, clinically significant bronchiectases, tumours).)
19. Immunological diseases or known infection with Human Immunodeficiency Virus (HIV).
20. Liver impairment Child-Pugh B/C and/or active viral hepatitis.
21. Severe acute infectious diseases.
22. Any diagnosis of a malignant disease (other than basal or squamous cell carcinoma) within five years before enrolment into the trial.
23. Excessive alcohol intake or drug/substance abuse within the past year.
24. Any history of allergies, suspected hypersensitivity and/or contraindication to local anaesthetics (e.g. xylocaine, lignocaine) and/or sedative agents (e.g. benzodiazepines, propofol, opioids) that would not allow adequate anaesthesia and/or bronchoscopy sedation. Suspected hypersensitivity to the trial treatment (Roflumilast) or ingredients thereof, or any other contraindication for the use thereof.
25. Female Subjects of childbearing potential, not using or not willing to continue using a medically reliable method of contraception for the entire trial duration, such as oral, injectable, or implantable contraceptives, or intrauterine contraceptive devices, unless they are surgically sterilized/hysterectomized or post-menopausal >1 year or who are not using any other method of contraception considered sufficiently reliable by the Investigator in individual cases.
26. Pregnancy, breast feeding, planned oocyte donation or oocyte implantation
27. Planned donation of germ cells, blood, organs or bone marrow during the course of the trial.
28. Participation in another clinical trial (use of investigational product or device) within 30 days preceding the baseline visit V0 or re-entry of Subjects previously enrolled in this trial (for exemption see Section 7.4).

29. Suspected inability to comply with trial procedures (e.g. repeated bronchoscopies, bronchial biopsy and sputum induction procedures, language problems, psychological disorders).
30. Suffering from any concomitant disease that might interfere with trial procedures or evaluations according to the Investigator's judgement.
31. Use of disallowed drugs.
32. Employee at the investigational site, relative or spouse of the Investigator.

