7.3 Randomization Criteria

Subjects must meet all the following randomization criteria at V2 to be eligible for randomization into the double-blind treatment period (V2 = randomization visit):

1. No COPD exacerbation between V0 and V2 (as defined by the need for oral or parenteral glucocorticosteroid intake and/or hospitalization).
2. Tablet compliance $\geq 80\%$ and $\leq 125\%$.
3. The admission criteria at inclusion are still met.

Only Subjects who meet all randomization criteria will undergo the first bronchoscopy / bronchial biopsy.

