9.1.9.2 Clotting Time and Platelet Count

Blood sampling will be performed at visits V0, V1, and V5. Analyses of the clotting screen (PT, APTT, TT, INR and platelet count) will be done by the Central Safety Laboratory. Blood samples will be handled and stored according to the instructions provided by the Central Safety Laboratory. All laboratory samples have to be clearly and fully labelled according to the Central Laboratory Manual. The laboratory reports received by fax from the Central Safety Laboratory will be reviewed, signed and dated by the Investigator and attached to the CRF (including corrected reports).

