Appendix E Laboratory and Vital Sign Alert Values (Sponsor defined)

HEMATOLOGY

Hemoglobin: male < 11.5 g/dL female < 9.5 g/dL
Erythrocytes: male < 3.5 $10^6/\mu\text{L}$ or > 7 $10^6/\mu\text{L}$ female < 3.0 $10^6/\mu\text{L}$ or > 6.5 $10^6/\mu\text{L}$
White Blood Cell Count (WBC): < 2,800/mm³ or > 16,000/mm³
Eosinophils: > 20%
Platelet Count: < 75,000/mm³ or > 700,000/mm³

CHEMISTRY

SGOT (ASAT): > 3x ULNR
SGPT (ALAT): > 3x ULNR
Gamma-GT: > 3x ULNR
Alkaline Phosphatase (AP): > 3x ULNR
CK: > 3x ULNR;
Creatinine: > 2x ULNR
Total Bilirubin: > 2x ULNR
Potassium: > 6.0 mmol/L or < 3.0 mmol/L
Sodium: > 150 mmol/L or < 130 mmol/L
Glucose: > 2 x ULNR

VITAL SIGNS

BP systolic: > 170 mmHg or < 85 mmHg
BP diastolic: > 105 mmHg
Difference systolic BP at Vx (increase or decrease) compared to pre-treatment > 40 mmHg
Resting Heart Rate: > 120 bpm or < 50 bpm
Difference HR at Vx (increase or decrease) compared to pre-treatment > 30 bpm

ULNR = Upper Limit of Normal range

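### Exclusion criterion 10 gives its platelet limit per mL, 1000-fold below the evidently intended limit per mm³

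*Protocol*

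**What the plan says.** Section 7.2, criterion 10, excludes subjects with "Suspicion or diagnosis of a bleeding disorders irrespective of its pathophysiological mechanism". Among its examples it names "Thrombocytopenia (platelets $< 50000/\text{mL}$) and platelet dysfunction (e.g. uraemia". No other part of the protocol restates or corrects this limit.

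Appendix E lists the sponsor's laboratory alert values, among them "Platelet Count: < 75,000/mm³ or > 700,000/mm³".

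Three further places make the limit operative:

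- Section 9.1.9.2 schedules blood sampling at V0, V1 and V5, and states: "Analyses of the clotting screen (PT, APTT, TT, INR and platelet count) will be done by the Central Safety Laboratory".
- Section 7.0 requires: "All entry criteria, including test results, need to be confirmed prior to randomization or first dose".
- Section 7.3 lists among the conditions to be met at V2, before the first bronchoscopy: "The admission criteria at inclusion are still met".

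**The concern.** Platelet counts are expressed per mm³ (equivalently per µL) or per litre, and the protocol itself uses per mm³ in Appendix E. The same kind of figure stated per mL is 1000 times smaller in real terms. A site applying the number literally would pass a subject with severe thrombocytopenia.

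Subject safety and correct eligibility are at stake. Section 9.1.15 calls for 2-3 lobar and 2-3 sub-segmental biopsies at each of two bronchoscopies. Section 6.2 names serious bleeding among the risks. Section 7.6 excludes anticoagulants and several antiplatelet drugs, while Section 7.7 still allows low-dose acetylsalicylic acid and NSAIDs as needed. Bleeding risk is thus a stated concern, and criterion 10 holds the only objective platelet limit for entry. The Appendix E value does not replace it: under Section 9.1.9, crossing an alert value after V0 leads to an adverse event record, not to exclusion.

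**Working it through.** **Inputs**

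- Written exclusion limit: 50,000 per mL (Section 7.2, criterion 10).
- Lower platelet alert value: 75,000 per mm³ (Appendix E).
- Conversion: 1 mL = 1000 mm³ and 1 L = 10⁶ mm³.

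**Step 1: the written limit in the unit of Appendix E**

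50,000 per mL ÷ 1000 = 50 per mm³. Per litre, 50 × 10⁶ = 0.05 × 10⁹/L.

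**Step 2: the limit if the unit were mm³**

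50,000 per mm³ × 10⁶ = 50 × 10⁹/L, or 50,000,000 per mL.

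**Step 3: size of the discrepancy**

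50,000 ÷ 50 = 1000.

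**Step 4: consistency with Appendix E**

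| Exclusion limit | per mm³ | Alert value ÷ exclusion limit |
|---|---|---|
| As written (per mL) | 50 | 75,000 ÷ 50 = 1500 |
| Read as per mm³ | 50,000 | 75,000 ÷ 50,000 = 1.5 |

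An entry limit somewhat below the alert value is coherent, because the two serve different purposes. An entry limit 1500 times below it is not.

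**Step 5: what the literal number does**

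Take an assumed count of 20,000 per mm³ (an illustration, not a figure from the protocol). That is 20,000 × 1000 = 20,000,000 per mL, and 20,000,000 ÷ 50,000 = 400. The subject lies at 400 times the written limit and does not meet the numerical exclusion.

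**Step 6: could this be a misread character?**

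The defect turns on one character, m against µ. The text at hand keeps the micro sign elsewhere: in the erythrocyte alert value of Appendix E (10⁶/µL, the same kind of expression), in the dose in Section 8.1.3 and in the volumes in Section 1.3.4 of Appendix H. That speaks against a misread here but does not prove it.

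**The case against.** The conversion is not in dispute. The case on the other side concerns the source, the intended value and the practical effect.

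1. **Source.** One misread character would remove the finding. This stands as a reservation, and it is why checking the printed page comes first.
2. **Intended value.** No section states 50,000/mm³. Appendix E shows that 50/mm³ cannot be meant, but it does not by itself fix the right limit. This is correct: the value is inferred from the written figure combined with the unit of Appendix E. The sponsor should confirm it when making the correction.
3. **Safeguards.** The number is a parenthesis within a broad exclusion of suspected or diagnosed bleeding disorders. Criterion 9 excludes "Clinically relevant abnormal laboratory values suggesting an undiagnosed disease requiring further clinical evaluation (as assessed by the Investigator", and criterion 30 leaves further room for judgement. Section 9.1.9 asks for retesting at V1 where needed and careful evaluation of the exclusion criteria. A V1 count below 75,000/mm³ must be recorded as an adverse event before the V2 biopsy. Section 9.1.9.2 has the investigator review and sign the clotting report. Appendix F defers the procedure if the investigator considers the subject unsuitable. All of this stands, and a severely thrombocytopenic subject would probably be noticed. But apart from the alert value, which does not exclude anyone, these safeguards rest on judgement. The one objective exclusion limit does no work as written. Because it directly qualifies the word thrombocytopenia, a literal reader could also take it to narrow the general wording.
4. **Weight.** Criterion 10 falls under the general-health criteria, whose violations Section 13.1.1.4 treats as minor by default, so the analysis does not depend on it. This is true, and no effect on the analysis is claimed.

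**Conclusion.** The limit is wrong as written. As it stands, criterion 10 sets 50 platelets per mm³, 1000-fold below the evidently intended 50,000/mm³, and the number alone would screen out practically no outpatient. It is an operative safety threshold, checked against central laboratory results before an invasive procedure, so it should be corrected. Section 14.2 allows no exemptions from the criteria, which is a further reason to have their wording right.

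The conclusion rests on two assumptions: that the printed protocol reads mL, as the text at hand does, and that the intended unit is the one in Appendix E. Confidence is medium because of the first. Practical harm is limited by the remaining safeguards. Power, type I error and the analysis are unaffected.

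**What to change.** Check the printed page. If it reads mL, change the limit in criterion 10 to < 50,000/mm³ (50 × 10⁹/L), in the same unit as Appendix E, with the sponsor confirming the value. The Appendix E alert value can stay at 75,000/mm³.

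The cost is one unit in one criterion. Procedures, data collection and analysis do not change, and the correction can be made with other typographical corrections in an amendment. If the printed page already reads µL, nothing need be changed, since 1 µL equals 1 mm³.
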